3.1 Benefits and Risks

This study is the first clinical trial in patients diagnosed with generalized pustular psoriasis on adalimumab in the world, and expected clinical use of this drug in Japan. The dose regimen planned in this study is 80 mg for initial loading dose subcutaneously followed by 40 mg every other week (eow) on and after Week 2 until study end, which is the same dose regimen in Ps approved in Japan. Dose escalation to 80 mg eow is allowed if subjects have inadequate response on or after Week 8 and meet the dose escalation criteria. Reasonable efficacy is expected not only in the patients who had inadequate response to the existing therapies, but also in the infliximab-secondary failures, which have been reported to being increased in Japan. The safety of this dose regimen is supported by the safety data of clinical studies in plaque psoriasis (Studies M04-688 and M04-702).

3.2 Adalimumab Overview

Adalimumab is a recombinant human immunoglobulin (IgG1) monoclonal antibody containing only human peptide sequences. Adalimumab is produced by recombinant deoxyribonucleic acid (DNA) technology in a mammalian cell expression system. It consists of 1330 amino acids and has a molecular weight of approximately 148 kilodaltons. Adalimumab is composed of fully human heavy and light chain variable regions, which confer specificity to human TNF, and human IgG1 heavy chain and kappa light chain sequences. Adalimumab binds with high affinity and specificity to soluble TNF- α but not to lymphotoxin- α (TNF- β).

TNF is a naturally occurring cytokine that is involved in normal inflammatory and immune responses. Elevated levels of TNF play an important role in pathologic inflammation. Adalimumab binds specifically to TNF and neutralizes the biological function of TNF by blocking its interaction with the p55 and p75 cell surface TNF receptors. Adalimumab also modulates biological responses that are induced or regulated by TNF. After treatment with adalimumab, levels of acute phase reactants of inflammation (C-reactive protein [CRP] and erythrocyte sedimentation rate [ESR]) and serum cytokines rapidly decrease.

Adalimumab was first approved in US and EU for the treatment of Rheumatoid Arthritis in 2002 and 2003, respectively, and subsequently the Pharmaceuticals and Medical Devices Agency in Japan in 2008. Additional indications have been approved in the US and EU including Psoriasis, Psoriatic Arthritis, Axial Spondylitis, Crohn's Disease, Juvenile Arthritis, and Ulcerative Colitis. Additional updates regarding approved indications can be found in the current edition of the Humira Investigational Drug Brochure.

3.3 Safety Information

Adalimumab therapy has a well-established and well-described safety profile based on extensive post-marketing experience and continued clinical trial subject exposure since the first approved indication in 2002 for rheumatoid arthritis. A detailed discussion of the

pre-clinical toxicology, metabolism, pharmacology, and safety experience with adalimumab can be found in the current Investigator's Brochure. AbbVie is committed to continue to collect safety information including those events that may occur in this trial in order to confirm this established safety profile and to identify any unknown potential adverse reactions, rare events and those events with a long latency. AbbVie is participating in a Food and Drug Administration (FDA)-requested, TNF inhibitor class wide exploration of the rare appearance of malignancy in subjects who are 30 years old or younger at the time of diagnosis. The risk of malignancy in this age group has not been established and is difficult to study due to its rarity. AbbVie appreciates your attention to the additional reporting requirements needed in this unlikely event, outlined in Section 6.1.5 under Adverse Event Reporting.

4.0 Study Objective

The primary study objective is to investigate efficacy, safety and pharmacokinetics of adalimumab in Japanese patients with generalized pustular psoriasis (GPP).

5.0 **Investigational Plan**

5.1 Overall Study Design and Plan: Description

This is a Phase 3, multicenter, open-label, single-arm study of adalimumab dosing regimens (80 mg at Week 0 by subcutaneous injection, followed by 40 mg every other week [eow] on and after Week 2 until Week 50) in Japanese patients with generalized pustular psoriasis with total skin score of at least 3 and erythema with pustule (skin score of at least 1) in Japan Dermatology Association (JDA) severity index of GPP in GPP Medical Care Guideline 2014. Dose escalation to 80 mg eow is allowed for subjects who do not have adequate response on or after Week 8.

The study is designed to enroll 10 subjects at approximately 10 sites in Japan to meet scientific and regulatory objectives in alignment with ethical considerations.

This study will include:

[figure not shown]
- A 30-day Screening Period
- A 52-Week Treatment Period
- A 70-Day Follow-Up Period

A subject's participation in the study is anticipated to be up to 66 weeks. There is a \pm 7-day window for all study visits. An effort will be made to bring subjects back to their original scheduled visit (calculated from Baseline) if they are out of the visit window.

Study visits for clinical and safety assessments will be performed at Baseline (Week 0), Weeks 2, 4, 8, 12, 16, 20, 24, 28, 32, 36, 40, 44, 48 and 52, and at the Premature Discontinuation visit if the subject discontinues prior to Week 52. No open label extension (OLE) study is planned after this 52-week study. Blood samples will be collected for clinical laboratory test, adalimumab serum concentrations, anti adalimumab antibody (AAA) levels, as indicated in [Table 1](#). In addition, photography of skin lesion will be performed in subjects who consent to it in pre-selected sites.

A schematic of the study design is presented in [Figure 1](#).

Figure 1. Study Schematic

Screening Period

The Screening Period begins at the Screening Visit and continues through to Baseline Visit (Week 0). Screening Assessments will include medical history, physical

examination, chest x-ray, electrocardiogram (ECG), laboratory results including pregnancy testing, all of which will be reviewed by the study site to confirm selection criteria are met prior to enrolling the subject.

Subjects who meet all eligibility criteria during the Screening Period (Section 5.2.1 and Section 5.2.2) will enter the 52-Week Treatment Period. The length of time between Screening and the Baseline Visits must allow time for lab results. The Screening period (30 days, \pm 7 days is granted around all study visits) may be extended as necessary for subjects who require initiation of prophylactic anti-tuberculosis (TB) therapy, or in case of external, not subject-related circumstances (e.g., due to delay of availability of screening test results).

Subjects who initially screen fail for the study may be permitted to re-screen following re-consent. There is no minimum period of time a subject must wait to re-screen for the study. The subject must meet all inclusion and none of the exclusion criteria at the time of re-screening in order to qualify for the study. If the subject had a complete initial screening evaluation including the assessment of a purified protein derivative (PPD) test (or equivalent), or Interferon-Gamma Release Assay (IGRA; QuantiFERON-TB Gold or equivalent), chest x-ray, and ECG, these tests will not be required to be repeated for re-screening provided the conditions noted in Section 5.3.1.1 are met and no more than 90 days have passed. All other screening procedures will be repeated. As appropriate, sites should contact the AbbVie SDP to confirm if subjects may be re-screened.

52-Week Treatment Period

Subjects who meet all of the inclusion criteria and none of the exclusion criteria will be enrolled into the 52-Week Treatment Period.

All subjects enrolled in the study will be allocated at Baseline (Week 0) to the same adalimumab dose regimen at the investigation site. The dose regimen will be 80 mg at Baseline (Weeks 0) by subcutaneous injection followed by 40 mg eow on and after Week 2 until Week 50 as shown in [Figure 1](#). Dose-escalation to 80 mg eow will be allowed for

subjects who do not have adequate response (e.g., minimal improvement, unchanged or worsened) on or after Week 8. No dose reduction is allowed after dose escalation.

Subjects will return to the study site at scheduled visits and complete study procedures for each visit as outlined in Section [5.3.1.1](#).

For subjects who are on oral steroids at the Baseline, their steroid dose must be tapered off for 4 weeks (until Week 4) and withdrawn for the rest of the study period. For subjects who are on cyclosporine at the Baseline, the treatment must be tapered off for 8 weeks (until Week 8) and withdrawn for the rest of the study period.

Throughout the study, subjects who are on etretinate (maximum dose of 20 mg/day at the Baseline), MTX, azathioprine, or salazosulfapyridine will be continued on their stable dose or have their dose of GPP-specific concomitant medications decreased as specified in Section [5.2.3.2](#). Dose escalation is not allowed for these treatments.

No study drug will be administered at the final visit.

70-Day Follow-Up/Premature Discontinuation

Subjects may discontinue adalimumab treatment at any time during study participation (Section [5.4](#)). Subjects who end study participation early will have a premature discontinuation (PD) Visit. All subjects will have a follow-up phone call approximately 70 days after the last administration of study drug to obtain information on any new or ongoing AEs.

5.2 Selection of Study Population

Ten subjects will be enrolled at approximately 10 investigation sites in Japan.

Male and female subjects who meet all of the inclusion criteria specified in Section [5.2.1](#) and none of the exclusion criteria specified in Section [5.2.2](#) of the protocol are eligible to be enrolled into the study.

5.2.1 Inclusion Criteria

1. Subject must be able and willing to provide written informed consent and comply with the requirements of this study protocol. If the subject is < 20 years old, a subject's parent or legal guardian must be willing to give written informed consent.
2. Male or female ≥ 15 and ≤ 75 years of age at the Baseline visit.
3. Subject must have a diagnosis of Generalized Pustular Psoriasis (GPP) for at least 60 days prior to Screening and determined by the Investigator through subject interview and review of medical history during the Screening Period.
4. Subject must have had an inadequate response to, or demonstrated intolerance to, or have a contraindication to the currently approved treatment for their GPP (excluding infliximab).
5. Subject must have total skin score of at least 3 and erythema with pustules (skin score of at least 1) in JDA severity index of GPP in GPP Medical Care Guideline 2014 in Japan at Baseline.
6. Subject may be included if they have previously experienced a benefit for their GPP from infliximab and discontinued its use due to a subsequent loss of response (i.e., judged by the Investigator to have responded to infliximab in the past and subsequently experienced an overall lack of improvement or worsening of GPP related symptoms, "infliximab secondary failure"), or intolerance (i.e., in the opinion of the investigator therapy was discontinued as a result of a significant acute or delayed infusion/administration reaction to the medication). Confirmed documentation indicating loss of response or lack of tolerability will be required, see Section 10.1 and [Appendix Q](#).
7. If female, subject is either not of childbearing potential, defined as postmenopausal for at least 1 year or surgically sterile (bilateral tubal ligation, bilateral oophorectomy and/or hysterectomy) or is of childbearing potential who must have negative result of pregnancy test performed at the Screening and at the Baseline. Female subject of childbearing potential is practicing an approved method of birth

control throughout the study and for 150 days after last dose of study drug.

Examples of approved methods of birth control which result in a low failure rate when used consistently and correctly are:

- Condoms, sponge, foams, jellies, diaphragm, intrauterine devices (IUDs), or intrauterine hormone releasing system (IUS);
- Sexual abstinence (when in line with preferred and usual lifestyle of the subject);
- A vasectomized partner;
- Hormonal contraceptives for at least 90 days prior to study drug administration.

Note: low-dose progestin-only oral contraceptives are not considered adequate.

8. If female, subject is not breast-feeding throughout the study and for 150 days after last dose.
9. Subject has a negative TB Screening Assessment (including a PPD test and/or Quantiferon TB Gold test, or equivalent) and negative chest x-ray (CXR) (posterior anterior [PA] and lateral view). If the subject has evidence of a latent TB infection, the subject must initiate and complete a minimum of 2 weeks of an ongoing TB prophylaxis or have documented completion of a full course of TB prophylaxis prior to Baseline (Section 5.3.1.1).
10. Subject is judged to be in good general health, as determined by the Principal Investigator based upon the results of a medical history, physical examination, laboratory profile, chest x-ray, and a 12 lead electrocardiogram (ECG) performed during the Screening.

Rationale for the Inclusion Criteria

- 1 In accordance with good clinical practice (GCP)
- 2 – 10 In order to select the appropriate subject population with a disease status representative of the target population for evaluation

5.2.2 Exclusion Criteria

1. Subject has erythrodermic psoriasis, guttate psoriasis, or subcorneal pustular dermatosis at Screening.
2. Subject diagnosed drug-induced GPP.
3. Total score of 14 or more in JDA severity index of GPP in GPP Medical Care Guideline 2014 in Japan.
4. Subject has other active skin disease (e.g., urticarial, atopic dermatitis) or skin infections (bacterial, fungal, or viral) that may interfere with evaluation of GPP, with the exception of footpad trichophytosis (athlete's foot).
5. Subject who cannot taper off cyclosporine until Week 8 after the Baseline and during the study. Subjects who cannot taper etretinate to 20 mg/day at the maximum dose prior to the Baseline.
6. Subject who is receiving oral corticosteroid more than 10 mg/day at the Baseline, and cannot taper off until Week 4 after the Baseline and during study.
7. Subject who received granulocyte and monocyte adsorption apheresis (GMA) therapy for at least 28 days prior to the Baseline and cannot avoid this therapy during the study.
8. Subjects who received any investigational agents of chemical or biologic nature (including anti-IL17 agents), which would be efficacious to GPP or psoriasis-related skin disease for at least 28 days or 5 half-lives of the drug prior to the Baseline, whichever is longer, and during the study.
9. Subjects who received ustekinumab for at least 84 days prior to the Baseline and during the study.
10. Subject who cannot avoid PUVA or narrow-band UVB phototherapy for at least 14 days prior to the Baseline and during the study.
11. Subject who cannot avoid "Strongest" corticosteroid in Japanese classification of topical therapy for at least 14 days prior to the Baseline and during the study.

12. Subject who cannot avoid anti-tumor necrosis factor (TNF) agent other than infliximab and adalimumab (including but not limited to etanercept [Enbrel], golimumab [Simponi] or certolizumab pegol [Cimzia]) for at least 28 days prior to the Baseline and during the study.
13. Prior exposure to adalimumab.
14. Subject who has previous used infliximab:
 - and has not clinically responded at any time ("primary non-responder") unless subject experienced a treatment limiting reaction, or
 - who used infliximab ("secondary treatment failure") within 42 days prior to the Baseline.
15. Prior exposure to medications that have a potential or known association with progressive multifocal leukoencephalopathy (PML) (i.e., natalizumab [Tysabri®], rituximab [Rituxan®], efalizumab [Raptiva®]).
16. Subject with any active viral infection that makes the subject an unsuitable candidate for the study based on the investigator's clinical assessment.
17. Hepatitis B: HBs Ag positive (+) or detected sensitivity on the HBV-DNA PCR qualitative test for HBc Ab/HBs Ab positive subjects.
18. Subject with known hypersensitivity to the excipients of adalimumab.
19. Positive pregnancy test at the Screening (serum) or the Baseline (urine).
20. Female who is breast-feeding or considering becoming pregnant during the study.
21. History of clinically significant drug or alcohol abuse in the last 12 months.
22. History of demyelinating disease (including myelitis) or neurologic symptoms suggestive of demyelinating disease.
23. History of moderate to severe congestive heart failure (NYHA class III or IV), recent cerebrovascular accident and/or any other condition which, in the opinion of the investigator, would put the subject at risk by participation in the study.

24. Current evidence of dysplasia or history of malignancy (including lymphoma and leukemia) other than a successfully treated non-metastatic cutaneous squamous cell carcinoma, basal cell carcinoma or localized carcinoma in situ of the cervix.
25. Chronic recurring infections or active TB.
26. Infection(s) requiring treatment with intravenous (IV) anti-infectives (antibiotics, antivirals, antifungals) within 30 days prior to Baseline or oral anti-infectives (antibiotics, antivirals, antifungals) within 14 days prior to Baseline.
27. History of invasive infection (e.g., listeriosis, histoplasmosis), human immunodeficiency virus (HIV).
28. Screening laboratory and other analysis show any of the following abnormal results:
 - AST, ALT $> 1.75 \times$ upper limit of the reference range;
 - WBC count $< 3.0 \times 10^9/L$;
 - Electrocardiogram (ECG) – with clinically significant abnormalities;
 - Total bilirubin ≥ 3 mg/dL; except for subjects with isolated elevation of indirect bilirubin relating to Gilbert syndrome;
 - Serum creatinine > 1.6 mg/dL.
29. Subject is considered by the Investigator, for any reason, to be an unsuitable candidate for the study.

Rationale for the Exclusion Criteria

1, 2	To avoid medical conditions that may compromise the ability to identify subjects with the correct diagnosis or to interpret medical importance of clinical results
3, 18, 21	To exclude subjects who maybe at increased risk for protocol non-adherence or premature discontinue
4 – 15	To avoid bias for the evaluation of efficacy and safety by concomitant or prior use of other medications or treatments

16, 17, 19, 20, To reduce the risk to subjects or others and/or to exclude underlying
22 – 28 conditions that would compromise the subject's safety

29 To maintain the integrity of other aspects of study conduct, including,
subject sampling, treatment procedures, etc.

5.2.3 Prior and Concomitant Therapy

5.2.3.1 Prior Therapy

Any non-GPP medication or vaccine (including over-the-counter or prescription medicines, vitamins, mineral supplements, and herbal supplements) that the subject is receiving within 30 days prior to Baseline, is receiving at the time of Enrollment, and/or receives during the study, must be recorded along with the reason for use, date(s) of administration including start and end dates, and dosage information including dose, route and frequency on the appropriate electronic case report form (eCRF). Medication for PPD test and injection solvents does not need to record as far as adverse events derived from these drugs are not occurred.

GPP-specific medications and therapies (including but not limited to cyclosporine, etretinate, MTX, oral or topical corticosteroids, topical vitamin D3, phototherapy, or GMA) that the subject has received within 90 days of Baseline should be recorded on the appropriate page of the eCRF and should include the date(s) of administration and dosages, and reason(s) for termination of the treatment (if appropriate). Subjects who failed to respond (within the past 1 year) or were intolerant (within the past 5 years) to treatment will have date(s) of administration, dosages including maximum dose, and reasons for discontinuation recorded in appropriate eCRF, as long as these information is available in the medical records.

For subjects previously treated with infliximab, the infliximab history will be recorded, including the duration of therapy, maximum dose, reason for use and reason(s) for termination of treatment.

The AbbVie SDP identified in Section [6.1.5](#) should be contacted if there are any questions regarding concomitant or prior therapies.

In addition for subjects age ≤ 30 with a reported malignancy adverse event, prior exposure to, or current use of, antineoplastics, or other drugs which have a risk of malignancy as stated in their labels and other relevant dosing information to estimate total exposure will be collected in the source documents and appropriate eCRF pages. At the time of the reported malignancy adverse event, sites will be asked if any of the prior and concomitant medications contributed to the event. Any medications used prior to the study will be captured on the appropriate eCRF. Information on the reason for use, date(s) of administration including start and end dates, highest maintained dose, dosage information including dose, route and frequency, and reason for stopping the medication will be collected in the source documents and appropriate eCRF pages.

5.2.3.2 Concomitant Therapy

Doses of etretinate (tapered to 20 mg/day at maximum dose prior to the Baseline), MTX, azathioprine, or salazosulfapyridine taken at Baseline will be continued and remain stable throughout the study. Doses may be decreased or terminated in the event of moderate-to-severe treatment-related toxicities or improvement of GPP skin lesion according to the discretion of the investigator. Dose escalation of these treatments will not be allowed.

Doses of topical corticosteroids ("Very strong," "Strong," "Medium" and "Weak" in Japanese classification), topical vitamin D3, or topical tacrolimus taken at the Baseline will be continued without dose escalation. Dose escalation (increase of amount for use) of topical corticosteroids is allowed only to use lower classes of drugs. Doses may be decreased or terminated in the event of moderate-to-severe treatment-related toxicities or improvement of GPP skin lesion according to the discretion of the investigator.

For subjects who are on oral steroids at the Baseline, their steroid dose must be tapered off for 4 weeks (until Week 4) and withdrawn for the rest of the study period. For subjects

who are on cyclosporine at the Baseline, the treatment must be tapered off for 8 weeks (until Week 8) and withdrawn for the rest of the study period.

Changes in all concomitant medications will be assessed at each study visit from Baseline (Week 0) through Week 52/PD Visits. Any changes will be documented, including the reason for the change of dose will be documented in the source documents and captured on the appropriate eCRF page.

Prophylaxis treatment with isoniazid for TB will be recorded. Even if a subject prematurely discontinues the study, isoniazid treatment should be continued for 9 months considering the best interest of the subject at the discretion of the investigator.

Any vaccine (except for live vaccines) administered during the study will be recorded in the eCRF as a concomitant medication.

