3.0 Introduction

Generalized Pustular Psoriasis (GPP) is severe form of psoriasis and inflammatory disease of undetermined cause, which is characterized by generalized cutaneous erythema along with acute pyrexia as well as multiple sterile pustules. This disease has a very low incidence in Japan, and the effective treatments are limited. Therefore, it is designated as a specified rare and intractable disease by the Ministry of Health, Labour and Welfare (MHLW).

GPP may either be preceded by plaque psoriasis, or arise without a prior history of plaque psoriasis, classically after withdrawal of systemic glucocorticosteroids,¹ and recently the studies for disease pathogenesis have been identified specific gene region susceptible to GPP.² GPP is characterized by pyrexia with chills and extensive skin erythema, where tender pustules form and then coalesce into lakes of pus. Desquamation from the pustules occurs thereafter, which is accompanied by nail plate changes (thickening and onycholysis), complaint of general malaise, and with a high frequency, mucosal symptoms, arthritis, and eye symptoms. These symptoms significantly impair quality of life (QOL) and markedly affect daily living. GPP is also characterized by multiple recurrences, and rarely, patients experience capillary leak syndrome, respiratory failure, or secondary amyloidosis, and are also at risk for death from cardiac or circulatory failure, general debility, and infections.

In the acute phase of the disease, GPP requires intense management of the general condition. Once the symptoms are relatively stable, management of skin symptom is important. In Japan, some systemic treatments are approved: etretinate, cyclosporine, and infliximab. All these treatments are demonstrated to be effective for GPP, and improve skin symptom and patient QOL. However, etretinate is teratogenic and causes liver disorder, while cyclosporine sometimes causes renal disorder and hypertension. For these reasons, their use cannot be continued for long-term disease management in some patients from the safety point of view. Infliximab, which contains murine protein, may rarely cause anaphylactic symptoms. Loss of response (secondary failure patients) has

been also observed during treatment for the long-term use, and actions to be taken for such reduced response are clinically significant. These limitations of current treatments highlight the need for new therapeutic options for GPP.

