5.3.3.2 Secondary Variables

Secondary efficacy variables, to be analyzed at each scheduled visit, include:

1. Proportion of subjects achieving Clinical Response (expect Week 16, which is the primary endpoint).
2. Proportion of subjects achieving remission.
3. Change from the Baseline in total GPP score (skin and systemic/laboratory test).
4. Change from the Baseline in JDA severity index of GPP.
5. Change and Percent change from the Baseline in total skin score.
6. Change from the Baseline in total systemic/laboratory test score.
7. Change from the Baseline in score of erythema area (overall) and BSA (BSA of GPP).
8. Change from the Baseline in score of erythema area with pustule and BSA.
9. Change from the Baseline in score of edema area and BSA.
10. Change from the Baseline in Body temperature.
11. Change from the Baseline in WBC.
12. Change from the Baseline in hs-CRP.
13. Change from the Baseline in serum Albumin.
14. Proportion of subjects achieving "Mild" in JDA severity index of GPP for patients with "Moderate" or "Severe" at the Baseline.
15. Proportion of subjects achieving Treatment Success in PGA (reduction of 2 grades).
16. Change from the Baseline in PGA grade.
17. Proportion of subjects achieving PGA 0/1 for patients with PGA grade at least 2 at Baseline.
18. Proportion of subjects achieving PASI 90.

19. Proportion of subjects achieving PASI 75.
20. Proportion of subjects achieving PASI 50.
21. Change and Percent change from the Baseline in PASI score.
22. Proportion of subjects achieving DLQI = 0.
23. Change from the Baseline in DLQI score.
24. Change from the Baseline in SF-36 score.
25. Proportion of subjects taking systemic co-medication for GPP (etretinate, MTX).
26. Proportion of subjects taking topical co-medication for GPP (corticosteroid, vitamin D3, tacrolimus).

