10.3 Secondary Efficacy Analyses

Discrete variables will be summarized by counts and percentages, and continuous variables will be summarized by descriptive statistics on the items below at each visit.

The subjects who have missing data for any reason such as early terminated subjects will be included into analysis using NRI for discrete variables or LOCF for continuous variables.

- Proportion of subjects achieving Clinical Response (expect Week 16, which is the primary endpoint).
- Proportion of subjects achieving remission.
- Change from the Baseline in total GPP score (skin and systemic/laboratory test).
- Change from the Baseline in JDA severity index of GPP.
- Change and Percent change from the Baseline in total skin score.
- Change from the Baseline in total systemic/laboratory test score.
- Change from the Baseline in score of erythema area (overall) and BSA (BSA of GPP).
- Change from the Baseline in score of erythema area with pustule and BSA.
- Change from the Baseline in score of edema area and BSA.
- Change from the Baseline in Body temperature.
- Change from the Baseline in WBC.
- Change from the Baseline in hs-CRP.
- Change from the Baseline in serum Albumin.
- Proportion of subjects achieving "Mild" in JDA severity index of GPP for patients with "Moderate" or "Severe" at the Baseline.
- Proportion of subjects achieving Treatment Success in PGA (reduction of 2 grades).
- Change from the Baseline in PGA grade.
- Proportion of subjects achieving PGA 0/1 for patients with PGA grade at least 2 at Baseline.
- Proportion of subjects achieving PASI 90.

- Proportion of subjects achieving PASI 75.
- Proportion of subjects achieving PASI 50.
- Change and Percent change from the Baseline in PASI score.
- Proportion of subjects achieving DLQI = 0.
- Change from the Baseline in DLQI score.
- Change from the Baseline in SF-36 score.
- Proportion of subjects taking systemic co-medication for GPP (etretinate, MTX, oral steroids, cyclosporine).
- Proportion of subjects taking topical co-medication for GPP (corticosteroid, vitamin D3, tacrolimus).

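### The two co-medication efficacy variables cannot separate reduced need from stopping for toxicity or a required withdrawal

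*Protocol*

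**What the plan says.** Protocol 5.2.3.2 gives three routes off background GPP therapy:

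- Etretinate, MTX, azathioprine and salazosulfapyridine are held stable, with one exception left to the investigator: "Doses may be decreased or terminated in the event of moderate-to-severe treatment-related toxicities or improvement of GPP skin lesion". The same sentence is repeated for topical corticosteroids, vitamin D3 and tacrolimus.
- Oral steroids taken at Baseline must be tapered off by Week 4 and stay off.
- Cyclosporine taken at Baseline must be tapered off by Week 8 and stay off.

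The section also requires changes to be recorded, "including the reason for the change of dose will be documented in the source documents", and on the eCRF.

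Protocol 5.3.3.2 introduces its list with "Secondary efficacy variables, to be analyzed at each scheduled visit, include". Item 25 is "Proportion of subjects taking systemic co-medication for GPP (etretinate, MTX", naming those two drugs only; item 26 is the topical counterpart. In SAP 10.3 the systemic variable has grown to "Proportion of subjects taking systemic co-medication for GPP (etretinate, MTX, oral steroids, cyclosporine", and the topical one is "Proportion of subjects taking topical co-medication for GPP (corticosteroid, vitamin D3, tacrolimus". The stated method is "Discrete variables will be summarized by counts and percentages". SAP 10.1 makes the efficacy analysis descriptive, sets no significance level and gives exact 95% confidence intervals for proportions.

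**The concern.** These variables sit in the efficacy list, where a falling proportion is naturally read as less need for other GPP treatment. That reading holds only for subjects who stopped because their skin improved. A subject who stops because of toxicity, or because the protocol required withdrawal, lowers the figure by the same amount. The trial has no control arm, so nothing in the table shows how much of a fall has which cause. Nor does a yes/no count register a dose reduction short of stopping, so part of any real reduction in need is not seen either.

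Toxicity stops are plausible on the protocol's own account. Section 3.0 says that "etretinate is teratogenic and causes liver disorder" and that long-term use is not possible in some patients for safety reasons. Treatment here runs for 52 weeks.

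**Working it through.** The plan states no figure for these variables. The power figures in protocol 8.2 concern the primary endpoint and play no part here; the only input taken from that section is the target of 10 subjects.

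**Step 1. Set the stopping rules beside the variables.**

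| Drug | Counted in | Routes off under protocol 5.2.3.2 | Does a stop show reduced need? |
|---|---|---|---|
| Etretinate, MTX | Protocol and SAP | Improvement or toxicity | Only if for improvement |
| Oral steroids | SAP only | Required by Week 4 | Not by itself |
| Cyclosporine | SAP only | Required by Week 8 | Not by itself |
| Topicals | Protocol and SAP | Improvement or toxicity | Only if for improvement |
| Azathioprine, salazosulfapyridine | Neither | Improvement or toxicity | Not counted |

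**Step 2. Size of one stop.** The proportion is k/n, with n = 10 if all enrolled subjects enter the FAS. One subject leaving the count changes it by 1/10 = 10 percentage points. If that subject still takes another drug on the list, the change is 0.

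**Step 3. Range under assumed use.** The documents give neither the number of Baseline users (b) nor the number of stops for reasons other than improvement (s), so both are assumed. I also assume no missing values, no improvement stops, and that each subject who stops takes no other listed drug. The proportion is then (b − s)/10:

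| b | s = 0 | s = 1 | s = 2 | s = 3 |
|---|---|---|---|---|
| 4 | 40% | 30% | 20% | 10% |
| 6 | 60% | 50% | 40% | 30% |
| 8 | 80% | 70% | 60% | 50% |

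Every fall in this table occurs without any subject needing less treatment.

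**Step 4. One figure, opposite histories.** Take b = 6 and three stops. The planned result is (6 − 3)/10 = 30%. The exact 95% interval runs from the 0.025 quantile of Beta(3, 8) to the 0.975 quantile of Beta(4, 7), that is 6.7% to 65.2%. The split of reasons (improvement/other) can be 3/0, 2/1, 1/2 or 0/3. All four print as 30% with the same interval, while the number who stopped for improvement is 3, 2, 1 or 0.

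**Step 5. Look for another output that separates them.** SAP 7.3 summarises prior and concomitant therapy by generic name only. SAP 11.2 tabulates and lists adverse events but does not link them to co-medication stops. No planned analysis uses the recorded reason for change.

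**The case against.** Much of the case on the other side stands, and it limits the point.

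- **Efficacy credit.** A reader might infer that a toxicity stop is scored as adalimumab efficacy. The documents do not say so. They attach no direction, responder rule or test to these variables, and SAP 10.1 makes them descriptive. Benefit is inferred from their place in the efficacy list.
- **Another legitimate reading.** The count also shows how many subjects were on background therapy when response was assessed. For that purpose actual use, whatever the reason for stopping, is the right measure. The addition of oral steroids and cyclosporine fits this reading, since both must be withdrawn anyway.
- **Direction of bias.** A reader might infer that the distortion always favours adalimumab. That is not supported beyond this count. A subject who loses a background drug to toxicity then has skin score, PGA and PASI assessed without it, which may count against adalimumab.
- **Hidden toxicity.** A reader might infer that the safety event goes unreported. Toxicity during treatment falls under the adverse event definition in protocol 6.1.1.1, and SAP 11.2 tabulates such events by term, severity and relationship and lists them.
- **Assumed inputs.** The user and stop counts are assumptions. The documents link liver disorder to etretinate, not to MTX. With an interval of 6.7% to 65.2% for 3/10, a 10-point shift supports no formal inference.

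None of this lets the planned count separate the reasons. If only a description of use is meant, the SAP does not say so. With 10 subjects and no comparator, the descriptive table is all the evidence there is on this question.

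**Conclusion.** The point holds as one of interpretation. As defined, the two variables give the same figure for reduced need, toxicity and protocol-required withdrawal. Each stop for a reason other than improvement moves the proportion by 10 percentage points, assuming 10 subjects in the FAS and no other listed drug in use by that subject. That step does not depend on the assumed number of users; the ranges in the tables do.

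The required withdrawals are the more certain part. Every Baseline user of oral steroids or cyclosporine who follows the protocol is off that drug by Week 4 or Week 8, so some fall in the SAP's systemic variable is built in wherever such a subject takes nothing else on the list. Toxicity stops are possible, but their number is unknown.

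The reach is limited to two of 26 descriptive secondary variables. The primary endpoint is untouched. The change is still worth making, because the reason is already collected and the efficacy reading depends on it.

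**What to change.** In SAP 10.3:

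1. Keep the count of actual use at each visit, systemic and topical.
2. Add rows, by drug, for Baseline users who have stopped or reduced, split by the reason recorded on the eCRF: improvement of GPP, toxicity, protocol-mandated taper, other.
3. State that any efficacy statement about reduced co-medication rests only on the improvement row.

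Do not recode subjects who stopped for toxicity or another reason as still taking the drug. That would misreport actual use, and it could show oral steroid or cyclosporine users as treated to Week 52 when the protocol requires them to be off.

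The cost is SAP wording and a small derivation from a field the protocol already requires. The documents do not show how that field is coded, so some mapping to the four categories may be needed. The efficacy reading may become less favourable. Nothing changes in data collection or clinical management.
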